### 4. STUDY DESIGN

This will be a single arm, controlled, blinded, multi-reader, multi-case (MRMC) study using a sequential design. The study will include 5-12 readers depending on qualifications and availability.

Imagio (IUS+OA) Training to be completed prior to any reads taking place. Read 1 is immediately followed by Read 2 within the same read session.

- Read 1 (Control): Mammogram (if available) + History + IUS (stills and videos provided), IUS Probability of Malignancy (POM) and BI-RADS scored and the data form locked.
- Read 2 (Test): Mammogram (if available) + History + IUS (stills and videos provided), and Imagio (IUS+OA) (stills and videos provided). An interim IUS POM and BI-RADS is recorded as well as a combined Imagio (IUS+OA) POM and BI-RADS Pre and Post SenoGram on separate data forms.

Read 1 reflects the information available to a radiologist when evaluating standard ultrasound images, taking under consideration the mass and patient history and assessing mammogram results as available. The History details to be provided are summarized under the Blinding section of the protocol. Read 1 (IUS reads) will serve as the control representing current clinical practice. Read 2 (IUS+OA) will be considered the test read and reflect a pre SenoGram IUS and Imagio (IUS+OA) POM and BI-RADS assessment in addition to a post SenoGram IUS and Imagio (IUS +OA) POM and BI-RADS assessment. Following the display of the SenoGram within the Post SenoGram data form, the IUS and OA feature scores are locked, and the reader is prompted to provide a Post SenoGram POM and BI-RADS. Once the Post SenoGram POM and BI-RADS are provided, the form is locked.

A total of 155 complete read sets from the original PIONEER Intention-to Diagnose (ITD) population will be randomly selected from within the PIONEER Study.

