- Comprising the 155 mass read sets, the first cohort will consist of 75 benign and 45 malignant masses (reflecting the same 37.5% prevalence of cancer as for the overall pivotal ITD population), classified by conventional diagnostic ultrasound (CDU) as BI-RADS 3 to 5 to be selected at random in proportion to the original assignment distribution of BI-RADS classifications among subjects in the PIONEER Study. To facilitate the alignment of the PIONEER Pivotal Study data with the Feasibility Study data, the mass image set sampling plan will select a proportion with and without mammograms depending on availability of the mammograms, separately for benign and malignant masses. Cohort 1 will be used for the effectiveness endpoint analyses in support of decision making. The same sampling strategy will be used to ensure a comparable proportion of mass image sets as for the PIONEER Pivotal Study.

- The second cohort consists of 30 additional malignant masses for which 1 or more pivotal study readers scored the mass a false negative during a read from the PIONEER study; this will assess if the excess FN rate observed with OA in the PIONEER study can be reversed.
- The third cohort will consist of five DCIS, lymphoma, or Phyllodes masses; this will assess how these atypical cases will be scored. Since there are so few of these cases, mammogram matching will not be possible.

This evaluation will further achieve the following:

1. The incremental contributions of IUS and Imagio (IUS+OA) by assessing the BI-RADS and POM values at each step in the read order traditionally used in clinical practice.
2. The SenoGram performance versus IUS and versus Imagio (IUS+OA) once IUS + OA features are scored with subset evaluation of the effect of presence or absence of the mammographic data on Senogram performance.

The SenoGram is a classification model that predicts the probability that a lesion is malignant for a given set of reader-assigned feature scores and other relevant data. For this study, the SenoGram will consist of two components, a user interface and a back-end computation engine. The reader will enter feature data into the user interface. When all data has been entered, but prior to a final submission of the data, the user interface will graphically display the model's predicted likelihood of malignancy [not to be confused with POM].

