The SenoGram figure will also display threshold lines that correspond to estimated sensitivities of 98%, 98.5%, 99%, and 99.5%, in relationship to the boundaries between BI-RADS categories. If the reader changes a feature score, the graphical display will automatically update with the revised prediction. The reader may optionally modify his or her BI-RADS and POM assignments based on the SenoGram predication; however, there is no requirement to do so. The use of the SenoGram result in decision making will be recorded for each reader for each image mass set evaluated. The SenoGram is trained on cases not selected for any Cohort of this study.

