
BI-RADS (BR): Downgrade (IUS+OA post) defined as:
 
 • IUS in BR 4a and IUS+OA post in BR 2-3 or • IUS in BR 3 and IUS+OA post in BR 2 
BI-RADS: Upgrade defined as:
 
 • IUS in BR 2 and IUS+OA post in BR 3-5 or • IUS in BR 3 and IUS+OA post in BR 4-5 
Tables will be repeated for IUS x IUS+OA post, IUS vs IUS+OA pre and IUS+OA pre vs IUS+OA post.
	
SAS: BI-RADS Grade Changes (Grouped BI-RADS), simple counts with 95% CI.
 
Benign+TPB: Reference PIONEER Table 14.2.13.4 [t_14_02_13_birch1_04]
 
Cancers: Reference PIONEER Table 14.2.13.7 [t_14_02_13_birch2_07]
 
Note: change from 99% CI to 95% CI

Net grade change – All masses – weight (W) that results in a significant OA+IUS vs IUS reflecting the FP advantage minus the weighted FN disadvantage.
	
SAS: PROC GENMOD and MIXED linear models will contrast difference in FN and FP to demonstrate clinical benefit.
 
Tables to be repeated for IUS x IUS+OA post, IUS vs IUS+OA pre and IUS+OA pre vs IUS+OA post

SenoGram performance using the following metrics from the study endpoints:
 
a) Sensitivity and specificity for SenoGram classification based on predicted probability and the SenoGram threshold, with separate analysis for each study cohort and with subgroup analysis for masses with and without mammogram BI-RADS data.
	
For each metric, a summary table for each reader (where appropriate) and for all readers to contain the following:
 
 • Measured value using Reader-01 feature data. • Estimated value from SenoGram cross-validation with PIONEER feature data. • Estimated value from SenoGram predictions for cohort masses with

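### Protocol Section 4 leaves unclear whether feature scores can still change once the SenoGram is on screen, and the SAP does not say which scores feed the SenoGram performance and feature-score analyses

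*Protocol*

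**What the plan says.** All the relevant protocol text is current wording in Section 4 (Study Design).

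- **Lock.** "Following the display of the SenoGram within the Post SenoGram data form, the IUS and OA feature scores are locked". The reader is then asked for the post-SenoGram POM and BI-RADS, after which the form itself locks.
- **Timing of the display.** "When all data has been entered, but prior to a final submission of the data, the user interface will graphically display" the model's prediction.
- **Content of the display.** It carries "threshold lines that correspond to estimated sensitivities of 98%, 98.5%, 99%, and 99.5%, in relationship to the boundaries between BI-RADS categories".
- **Update.** "If the reader changes a feature score, the graphical display will automatically update with the revised prediction".
- **What the reader may revise in response.** "The reader may optionally modify his or her BI-RADS and POM assignments based on the SenoGram predication". Feature scores are not named in that sentence.
- **Input to the model.** The SenoGram "predicts the probability that a lesion is malignant for a given set of reader-assigned feature scores and other relevant data".
- **Forms.** Read 2 records a "combined Imagio (IUS+OA) POM and BI-RADS Pre and Post SenoGram on separate data forms". No separate pre-display set of feature scores is mentioned.

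SAP Section 1.1.7, Table 1, reports three values for each SenoGram performance metric. The first is "Measured value using Reader-01 feature data". The second is an estimate from cross-validation on PIONEER feature data. The third comes from SenoGram predictions for the cohort masses using PIONEER data. Table 1 also summarises OA feature-score distributions for Cohort 1 as an exploratory analysis.

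**The concern.** The model's input is the reader's feature scores. If a reader can change those scores while looking at the model's output, the input to the SenoGram can depend on the SenoGram itself. Its measured sensitivity, specificity, specificity at 98% sensitivity and partial AUC would then partly reflect how the reader responded to the display.

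Three parts of the plan would be affected:

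- SAP Section 1.1.7.2 separates how readers use the SenoGram from whether its predictions are correct. Edits made after display would mix the two.
- Protocol Section 2.2 makes the comparison with cross-validation and hold-out estimates a secondary endpoint. Scores edited in view of the prediction are a different kind of input from the feature data behind those estimates.
- Protocol Section 1.2 uses SenoGram performance to decide whether the model is adjusted before the pivotal study, so a distorted figure could lead to a wrong decision there.

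The benign-versus-malignant feature-score distributions rest on the same scores.

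**Working it through.** No sample size, power or alpha figure is involved. The check is a comparison of texts, followed by a small calculation for scale.

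**Step 1: put the Section 4 statements in time order.** Data are entered, the prediction is displayed before final submission, the feature scores lock following the display, the post-SenoGram POM and BI-RADS are given, and the form locks. Because the display appears only once all data are in, an update triggered by a changed score must describe a change made while the prediction is visible. The open question is whether any interval for such a change exists between display and lock.

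**Step 2: test the two readings.**

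- *Reading A: scores lock as soon as the display appears.* The update sentence then has nothing to act on during study reads. There is no contamination, but the protocol describes a function that cannot operate.
- *Reading B: display, then optional edits, then lock.* The sentences can coexist. The locked scores may then have been changed with the prediction and the sensitivity lines in view.

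**Step 3: look for text that settles it.** Protocol Section 7.1 describes a lock at the reader's electronic sign-off of the case, which comes too late to help. Section 4 records whether the SenoGram was used in decision making, and SAP Section 1.1.7.2 summarises reported use and confidence. Neither records a change to a feature score. Nothing defines an edit interval, keeps a pre-display copy or flags edits, and the SAP does not say which version of the scores it analyses.

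**Step 4: trace which outputs are exposed under reading B.**

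| Output | Source | Exposed? |
|---|---|---|
| SenoGram metrics, value from this study | Feasibility readers' feature scores | Yes |
| SenoGram metrics, cross-validation value | PIONEER feature data | No |
| SenoGram metrics, predictions for cohort masses | PIONEER data | No |
| OA feature-score distributions | Feasibility readers' feature scores | Yes |
| IUS POM and BI-RADS, Read 1 | Form locked at Read 1 | No |
| IUS+OA pre POM and BI-RADS | Separate pre-SenoGram form | No |
| IUS+OA post POM and BI-RADS | Given after the SenoGram by design | SenoGram influence is intended |

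**Step 5: scale.** Cohort 1 has 45 malignant and 75 benign masses.

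- One malignant mass crossing the threshold for one reader: 1/45 = 2.2 percentage points of sensitivity. The 95-99% window is 4 points wide, and 2.2/4 = 0.56 of it.
- One benign mass crossing: 1/75 = 1.3 points of specificity.
- Malignant masses missed at 98% sensitivity: 45 × 0.02 = 0.9, so less than one mass per reader.
- Cohort 1 reader-mass records: 120 × 5 = 600 to 120 × 12 = 1,440. Over all 155 masses: 155 × 5 = 775 to 155 × 12 = 1,860.

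The record counts show where an edit could occur under reading B. They are not effect sizes, and under reading A the exposed number is zero. The per-mass figures show how much one edit could move a single reader's result. They do not say how often edits happen or in which direction.

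**The case against.** The strongest reply is that the lock sentence says following the display, not at the moment of display. A sequence of display, edit and lock fits that wording and also fits a display placed before final submission. On this view there are not two incompatible rules, only an unspecified interval. This is fair, and a reader who infers a strict contradiction goes further than the text allows. But it does not remove the problem, because the reading that reconciles the sentences is the one that permits edits in view of the prediction.

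Second, the sentence on what readers may revise names only BI-RADS and POM, and the update sentence describes how the display behaves without inviting readers to rescore. That stands. A reader might infer that feature scores will be tuned until the prediction agrees with the reader's opinion. The documents neither describe nor encourage this, so contamination is possible rather than established.

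Third, a reader might infer that every SenoGram performance figure is compromised. Two of the three values per metric come from PIONEER data and do not depend on edits made here. The third of them, predictions for the same cohort masses, even offers a reference against which a shift might be noticed. It could not separate the effect of edits from ordinary differences between the two sets of readers' scores.

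Fourth, the study is unpowered, has no formal hypotheses and treats its p-values as descriptive, and the primary comparison of IUS+OA post with IUS is meant to include SenoGram input. This limits the consequences to secondary and exploratory results. The decision on adjusting the model still draws on those results.

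Last, the Independent Review Charter or the eCRF build may fix the sequence. Neither is available here. Even if one does, the protocol and SAP should agree with it.

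**Conclusion.** The point holds in a conditional form. Section 4 of the protocol is inconsistent, or at best ambiguous, on when feature scores become final relative to the SenoGram display, and the SAP does not name the version it analyses. Bias arises only if scores can be edited after display and the edited scores are the ones analysed. In that case the exposed results are the value from this study's feature data within each SenoGram performance metric, its comparison with PIONEER cross-validation, and the exploratory OA feature-score distributions.

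The documents do not support a claim that contamination will occur, that all SenoGram metrics are affected, or that the IUS read or the pre-SenoGram assessments are compromised. The size and direction of any bias cannot be derived, since nothing is said about how often scores would be edited. The matter should still be settled before reads begin, because pre-display scores that were not captured cannot be recovered afterwards.

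**What to change.** 1. **Protocol Section 4:** replace the separate statements with one sequence that says when feature scores lock relative to the first display and whether the update function is active during study reads.
2. **eCRF:** store the feature scores as they stand immediately before the SenoGram is first shown. This can be done by locking them at that point or, if the update function stays, by keeping a time-stamped copy with an audit trail of later changes. Removing the update function is one option and is not required; the stored copy protects the endpoints equally well.
3. **SAP Table 1 and Sections 1.1.7.1 and 1.1.7.2:** state that the SenoGram performance value from this study and the feature-score analyses use the pre-display scores. If later edits are kept, they can be summarised under reader utilization.

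The cost is an eCRF setting and a few sentences in each document. No additional reads, masses or readers are needed.

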## **5. SELECTION OF READERS**

### **5.1 Reader Qualification Criteria**

- Completed residency and are board certified in radiology
- Active breast imager for at least 3 years.
- Readers to meet mammography interpretation requirements per mammography Quality Standards ACR (MQSA) for the year prior to study.
- Readers to meet breast imaging ultrasound interpretation requirements per ACR. for year prior to study.
- For the clinical study, a willingness to use BI-RADS 4 sub categories
- For the clinical study, the ability to participate and read all masses in both IUS and OA/US reader sessions.

## 5.2 Reader Training

### Imagio (IUS+OA) Training Summary Reader 01 Study

1. Didactic training module (4 hours)
  - a) Fundamentals of OA (*Questions and Answers*)
  - b) OA feature scoring (*Questions and Answers*)
  - c) OA-histologic correlation (*Questions and Answers*)
  - d) OA artifacts and Scan Techniques (*Questions and Answers*)
  - e) IUS feature scoring, including Importance of BI-RADS 4 subcategories, NLR and Bayes Theorem (*Questions and Answers*)
  - f) Pivotal Study False Negative and False Positive analysis (*Questions and Answers*)
  - g) The SenoGram and How to Use It
  - h) Summary (*final questions and comments*)
2. Interactive reading case module (*estimate 5 cases per hour, 4-6 hours*)
  - a) Mixture of benign and malignant enriched to 50% malignant
  - b) Mixture of cases with good, average, and below average reader performance – will start with easy cases, move to average cases, and finish with most difficult cases
  - c) Some malignant masses that caused false negative Pivotal study OA reads
  - d) Readers will learn to use reading station, draw ROIs, score features, and use the OA and combined OA-IUS SenoGrams to predict OA POM and BI-RADS category and downgrade
  - e) Each case will be read and scored by trainees, and then the Seno instructor will review how and why he/she would score the case, and finally review the histology and discuss concordance or discordance of OA feature scoring with the histology.
3. Test Cases - 30 (7.5 hours) 4 cases an hour
  - a) Mixture of benign (18) and malignant (12) masses, same prevalence as overall Pivotal ITD population
  - b) Mixture of easy, average, and difficult cases based upon Pivotal study reads
  - c) Some masses that caused false negative pivotal study Imagio (IUS+OA) reads
4. Pass / Fail criteria

Readers reading must pass a proficiency test before starting their study reads. If this is not achieved the first time the reader takes the test, the reader will be given targeted remediation training to their deviations and a second opportunity to take the test on a different set of test cases. The reader will proceed to read cases whether or not they pass the second test. If they fail the second test, remediation will take place before they start the study reads.

## 6. SELECTION OF READER SETS

### 6.1 Inclusion Criteria

*Reader sets must meet all the following inclusion criteria to be included in this study:*

- One analyzable mass per patient
- DCIS, lymphoma, and phyllodes masses to be looked at separately
- BI-RADS 3 and 4a, 4b, 4c and 5 masses as declared by clinical site investigator via PIONEER study conventional diagnostic ultrasound (CDU)
- Masses declared to be ITD
- Evaluable mammograms for a percentage of cases
- Patient age, indication and history available
- Evaluable OA and IUS video loops and stills

### 6.2 Exclusion Criteria

*Reader sets must be excluded if any of the following criteria are met:*

- Critical missing views for mammogram cases, IUS or OA stills and video that would preclude case from being evaluated by readers
- Mammogram, IUS or Imagio (IUS+OA) image quality inadequate due to error in labeling or positioning or acquisition technique
- Masses from multiple mass cases incorrectly labeled.
- Reader training cases

### 6.3 Reader Set Selection Procedure

- BBRF will select the mass sampling strategy taking training cases and cohort requirements into consideration
- BBRF will prepare the mass read order for Part 2 of the study.
- All image sets will be de-identified.

## 7.0 READER STUDY PROCEDURES

### 7.1 Reader Study Process Work Flow

Figure 1 below illustrates, at a high level, the central reader study process flow. Seno Medical will electronically transfer image sets to ACR-CRI. Upon receipt of the images at ACR CRI, imaging support staff will upload images to **T**ransfer of **I**mages and **D**ata [TRIAD], ACR's electronic image submission tool.

The images automatically undergo a de-identification process in TRIAD™, whereby all personal identifier DICOM tags in the image metadata are de-identified according to TRIAD™'s anonymization profile. If any personal identifiers are burned into exams received, ACR CRI staff will remove that by pixel cleaning. ACR-CRI imaging technologists will first perform quality control (QC-1) to document an inventory of all exams and their attributes.

ACR-CRI contracted multiple mass quality control reviewer will assess the image sets (QC-2) for inclusion by identifying and labeling Mass 1 on all modalities submitted for a given subject case where multiple masses are present. The acceptable image sets from the ACR QC (QC-1 and QC-2) process will be approved by BBRF and considered ready for central read.

BBRF will generate the study mass randomization scheme for the study.

The QC-1 and QC-2 checks will be documented in study specific procedure documents and outputs of such checks documented on study specific forms, all of which will be archived in an electronic Trial Master File (eTMF) and ACR CRI clinical databases.

ACR research staff serving as read monitors will be present during read sessions to ensure the read sequence is maintained, eCRFs are fully completed by the reader, cross-check the assigned read list with completed eCRFs and assist in any workstation-related questions. The read monitors will relay any issues they cannot resolve to the ACR Project Manager for remediation.

For the Feasibility Reader Study, a manual process of data entry will be performed. In order to maximize both workflow efficiency and data integrity, this process will be achieved by using the combination of the reader and a read monitor, working together as a team. Both the reader and the read monitor will be trained on the data entry process prior to production subject case assessments. The process of data entry is outlined below.

1. Read monitor calls out the Read ID to be reviewed based on the provided Reader Work List. The reader opens the Subject image case in the image viewing workstation. The read monitor opens the Subject eCRF case in the Rave Electronic Data Capture (EDC) Database. The reader calls out the Subject ID for the opened case as confirmation that it corresponds to the Subject ID opened in the eCRF database by the read monitor.
2. Reader performs the specified subject's image review using the designated Workstation and following assessment criteria as trained on for this study.
3. Read monitor prepares to perform data entry for the specified subject.
4. When the reader is ready to provide the data for data entry, the reader verbally notifies the read monitor.
5. The reader verbally provides the answers to each of the eCRF required field entries.
6. As the read monitor performs the manual data entry for each of the sequential fields directed by the flow of the eCRF, the read monitor verbally calls out their entry which is then verbally confirmed (or corrected, as necessary) by the reader.
7. This process will be repeated until all the appropriate fields for each of the required eCRFs are completed.

[figure not shown]
The reader electronically signs off on the data for a subject case at the completion of his/her review. It is understood that the commitment of a reader's electronic signature on the eCRF signifies that the assessment of the corresponding randomization ID is complete and accurate and is an attestation that no changes/edits need to occur.

The read monitor should be attuned to reader performance and suggest breaks as necessary to avoid reader fatigue.

As per the image review and data entry workflow described in this Protocol, once a subject scan review is completed by a reader, the reader provides their electronic signature and the eCRF is 'locked', preventing further changes.

Upon completion of all central read assessments by all readers, ACR-CRI will transfer the readers' results to Seno Medical's portal. BBRF will have access to the portal for purposes of conducting the statistical analyses.

